1. OBJECTIVES

1.1. Primary Objective

The primary objective of this study is to evaluate the severe and life-threatening toxicity rate observed in metastatic or unresectable soft tissue sarcoma subjects treated with doxorubicin and pembrolizumab, and compare to historical control.

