8. DATA AND SAFETY MONITORING PLAN

8.1. Safety Monitoring

This protocol will be monitored according to the processes in effect for all Levine Cancer Institute investigator-initiated studies and the protocol-specific monitoring plan, and will abide by standard operating procedures set forth by both the Carolinas HealthCare System Office of Clinical and Translational Research and the Levine Cancer Institute Clinical Trials Office. It is the responsibility of the Sponsor-Investigator to monitor the safety data for this study. The Sponsor-Investigator, Statistician, and other team members as needed will meet regularly to monitor subject consents, enrollment and retention, safety data for all subjects [including adverse events (AEs) for all grades and attributions, serious adverse events (SAEs)], study drug administration, and validity/integrity of the data. Documentation of these meetings will be kept with study records. SAEs will be reported to the Food and Drug Administration (FDA) and the IRB per their requirements. Major protocol deviations that result in a threat to subject safety or the integrity of the study will be reported to the IRB per their requirements. The Sponsor-Investigator will submit data to the LCI

Data and Safety Monitoring Committee according to the protocol-specific Data and Safety Monitoring Plan.

The Sponsor-Investigator will monitor the study accrual data regularly.

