10.6. Serious Adverse Event Definition

An AE or SAR is to be considered serious if the Investigator deems it as such and the event results in any of the following outcomes:

- Death;
- Life-threatening situation (patient is at immediate risk of death);
- Inpatient hospitalization or prolongation of an existing hospitalization (excluding those for study drug administration, protocol-related procedures,

palliative or hospice care, or placement of an indwelling catheter, unless associated with other serious events);

- Persistent or significant disability/incapacity;
- Congenital anomaly/birth defect in the offspring of a subject who received study treatment;
- Development of a new cancer (that is not a condition of the study)
- Overdose of pembrolizumab as defined in Section 6.9, that is associated with an adverse event even if no other seriousness criteria are met;
- Other: Important medical events that may not result in death, be immediately life-threatening, or require hospitalization, may be considered an SAE when, based upon appropriate medical judgment, they may jeopardize the subject or may require medical or surgical intervention to prevent one of the outcomes listed in this definition.
 - **Examples of such events are:**
 - Intensive treatment in an emergency room or at home for allergic bronchospasm;
 - Blood dyscrasias or convulsions that do not result in hospitalization;
 - Development of drug dependency or drug abuse.
 - An AE or SAR is to be considered life-threatening if the Investigator deems it as such and the event poses an immediate threat of death.

Pregnancy and Lactation

Although pregnancy and lactation are not considered adverse events, pregnancies and lactations must be reported from informed consent through 120 days after last dose of pembrolizumab, or 30 days if the subject initiates new anti-cancer therapy, whichever is earliest. All reported pregnancies must be followed to the completion/termination of the pregnancy. Pregnancy outcomes of spontaneous abortion, missed abortion, benign hydatidiform mole, blighted ovum, fetal death, intrauterine death, miscarriage and stillbirth must be reported as SAEs. If the pregnancy continues to term, the outcome (health of infant) must also be reported.

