12.2. Endpoint Definitions

12.2.1. Severe or Life-Threatening Adverse Event

Severe or life threatening adverse event will be determined for each subject indicating whether or not the event meets all criteria listed below:

- Meets the definition of seriousness as defined in Section 10.6, and
- Pembrolizumab-related or doxorubicin-related toxicity per the Sponsor-Investigator and
- Considered to be clinically significant by the Sponsor-Investigator as to contribute to the stopping rule.

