12.5. Primary Analysis

A maximum of 30 evaluable subjects with soft tissue sarcoma will be enrolled as a single cohort. It is not anticipated that the addition of pembrolizumab to standard chemotherapy will increase the rate of severe or life-threatening toxicity. It has been reported that the rate of any severe or life-threatening toxicity of doxorubicin and dacarbazine every 3 weeks is 55%⁴⁸.

If it becomes evident that the rate of severe or life-threatening toxicity convincingly exceeds 55%, enrollment to the study will be halted.

The stopping rule will hold enrollment if the posterior probability of severe or life-threatening toxicity risk exceeding 0.55 is 75% or higher. In this event, data will be evaluated to inform the subsequent conduct of the study. The prior for this monitoring rule is beta (11,9). This means that our prior assumption regarding the proportion of severe or life-threatening toxicity is 0.55, and there is 90% probability that this proportion is between 0.368 and 0.726. The operating characteristics of the stopping rule are given in Table 11 and are based on 5000 simulations:

Table 11. Operating characteristics of the stopping rule

Number of Subjects with Severe or Life-Threatening Toxicities	Max. Denominator Cutoff for Early Stopping	Posterior Probability: $\Pr(\text{Risk} > 0.55 \text{Data})$
4	4	0.7834
5	6	0.7536
6	7	0.8056
7	9	0.7728
8	11	0.7694
9	13	0.7558
10	14	0.7944
11	16	0.7812
12	18	0.7592
13	19	0.8002
14	21	0.7818
15	23	0.7710
16	25	0.7594
17	26	0.7988
18	28	0.7828
19	30	0.7706

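### The third criterion in Section 12.2.1 is an undefined Sponsor-Investigator judgment that can only remove serious, drug-related toxicities from the primary endpoint and the stopping count, with no required record or independent review

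*Combined protocol and SAP*

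**What the plan says.** Section 12.2.1 defines the endpoint for each subject by "indicating whether or not the event meets all criteria listed below", so the three bullets are cumulative:

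1. "Meets the definition of seriousness as defined in Section 10.6". Section 10.6 itself begins "An AE or SAR is to be considered serious if the Investigator deems it as such" and then requires one of the listed outcomes.
2. "Pembrolizumab-related or doxorubicin-related toxicity per the Sponsor-Investigator".
3. "Considered to be clinically significant by the Sponsor-Investigator as to contribute to the stopping rule".

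Section 1.1 makes this rate the primary objective, to evaluate and "compare to historical control". Section 12.5 gives the historical figure as 55% and sets the rule: "The stopping rule will hold enrollment if the posterior probability of severe or life-threatening toxicity risk exceeding 0.55 is 75% or higher". The prior is Beta(11,9), the maximum is 30 subjects, and Table 11 lists the cutoffs. Section 12.4.1 says the rule is assessed continuously. On oversight, Section 8.1 states: "It is the responsibility of the Sponsor-Investigator to monitor the safety data for this study". It also provides for regular meetings that include the statistician, and for data submission to the DSMC under a separate plan.

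**The concern.** Bullet 3 is circular: an event contributes to the rule if it is judged that it should contribute. The documents attach no definition of clinical significance, no grade threshold and no event list. Nor do they ask for a log of excluded events or name anyone who reviews the exclusions.

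The filter works in one direction. It acts only on events that have passed bullets 1 and 2 and cannot add an event that failed them, so any error it introduces lowers the counted rate. The person applying it also monitors the safety data, under a rule assessed continuously against a printed boundary, and so can know how far the count is from the next cutoff.

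Two things are at stake. One is whether the enrollment hold is triggered when it should be. The other is the primary comparison, in which a filtered rate is set against a benchmark that Section 12.5 describes as the rate of *any* severe or life-threatening toxicity.

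**Working it through.** **Inputs (Section 12.5).** Prior Beta(11,9); threshold rate 0.55; hold when the posterior probability is at least 0.75; maximum n = 30; the 16 cutoffs in Table 11.

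**Step 1: reproduce the plan's figures.** With x counted subjects out of n,

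Pr(p > 0.55 | x, n) = 1 − F(0.55; 11 + x, 9 + n − x),

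where F is the beta distribution function. The prior mean is 11/20 = 0.55 and the prior 90% interval is 0.368 to 0.726, both as stated. All 16 posteriors in Table 11 reproduce to within 0.014. The largest gap is at 7/9 (exact 0.7865, printed 0.7728), and gaps of this order are consistent with 5000 simulations. At 9/13 the exact value is 0.7488, so that row is on the list only through simulation error; this does not affect the point.

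**Step 2: leave out one subject at each cutoff.** Replace x by x − 1 with n unchanged:

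Pr(p > 0.55 | x − 1, n) = 1 − F(0.55; 10 + x, 10 + n − x).

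| Table 11 row | Exact posterior | One subject not counted |
|---|---|---|
| 4/4 | 0.780 | 0.636 |
| 5/6 | 0.758 | 0.616 |
| 10/14 | 0.794 | 0.680 |
| 13/19 | 0.801 | 0.697 |
| 17/26 | 0.794 | 0.699 |
| 19/30 | 0.767 | 0.670 |

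Over all 16 rows the result runs from 0.616 to 0.699, always below 0.75. This step needs no assumption about how often the filter is used.

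**Step 3: effect on the chance of a hold (hypothetical).** Let p be the true share of subjects with a serious, drug-related toxicity and f the share of those subjects whom bullet 3 leaves uncounted. The counted rate is p(1 − f). The probability of a hold by n = 30 comes from an exact forward recursion with a look after each subject, holding at the first n where the exact posterior reaches 0.75. The earliest possible hold is 4/4. With p = 0.70:

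| f (assumed) | Counted rate | P(hold) | P(hold), Table 11 cutoffs as printed |
|---|---|---|---|
| 0 | 0.70 | 0.912 | 0.914 |
| 1/5 | 0.70 × 0.8 = 0.56 | 0.474 | 0.482 |
| 1/3 | 0.70 × 2/3 = 0.467 | 0.19 | 0.20 |

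The two boundaries differ only at n = 13.

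**Step 4: sensitivity to the unit.** The endpoint is per subject, so f must be a share of subjects. If 1 *event* in 5 were removed and events per subject were Poisson (also an assumption), then λ = −ln(0.30) = 1.204. The counted rate would be 1 − exp(−0.8 × 1.204) = 0.62, with P(hold) 0.69. Removing 1 event in 3 gives 1 − exp(−1.204 × 2/3) = 0.55, with P(hold) about 0.45. The loss is smaller because a subject with several events stays counted unless all of them are removed.

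**Step 5: the rule with nothing removed.** At a true rate of exactly 0.55 the same recursion gives P(hold) = 0.44.

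**The case against.** A reader might infer that the Sponsor-Investigator can switch off safety oversight event by event. The documents do not support that. The statistician and team review AEs of all grades and attributions, and data go to the DSMC (Section 8.1). SAEs are reported to the IRB and to the drug's manufacturer, and serious unexpected events to the FDA (Sections 10.9 to 10.11). Several of these bodies can discontinue the study for safety (Section 13.1), and safety findings are grounds for termination (Section 13.2). Section 12.7 summarizes SAEs unfiltered, and attribution is recorded for every event (Section 10.3.1), so an unfiltered related-SAE rate could be derived. Nothing suggests intent or actual misuse, and seeing the data is inherent in a single-arm trial. What stands against the objection is that none of these provisions gives anyone a role in reviewing a bullet 3 exclusion. The DSMC plan is not among the documents, so what it adds cannot be checked.

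A second objection is that bullet 3 does useful work, and this is partly right. Seriousness under Section 10.6 is not severity: an overdose with any adverse event qualifies, and Table 7 counts a precautionary admission. Simply deleting the bullet would let a related but non-severe SAE count as severe or life-threatening. It would not turn the endpoint into one based on CTCAE grade, since Section 12.2.1 names no grade. It would also leave judgment in bullet 2 and in Section 10.6, although those have written definitions and bullet 3 has none. This argues for replacing the bullet rather than merely deleting it.

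Third, the hold probabilities above are not the plan's. Table 11 gives cutoffs and posteriors only, so it cannot be said that a stated hold probability is wrong. How the cited trial counted toxicity is not visible either; the contrast with the benchmark rests on the protocol's own description.

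**Conclusion.** The concern holds as a defect of definition. The primary endpoint and the stopping count pass through a circular, undefined, one-directional judgment, with no required record and no independent review. That much follows from the text. The result that one uncounted subject at any Table 11 row leaves the posterior below 0.75 is exact.

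The fall in the chance of a hold from 0.91 to 0.47 or 0.19 is illustrative. It rests on an assumed true rate of 70%, on assumed shares of 1 in 5 or 1 in 3 qualifying subjects not counted, and on a look after every subject. The documents do not indicate how often the criterion would remove a subject. The defect concerns the formal count and the comparison with 55%; it does not show that safety reporting as a whole is compromised.

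**What to change.** Replace the third bullet of Section 12.2.1 with an objective severity criterion fixed in advance, using the CTCAE grade already recorded (Table 7: Grade 3 severe, Grade 4 life-threatening, Grade 5 death). State whether Section 10.6 seriousness is still also required, because using grade alone would redefine the endpoint. Apply the criterion to events with recorded attribution to either drug. Move any judgment of clinical significance to the data review that Section 12.5 already provides once a boundary is crossed.

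If some discretionary exclusion is kept, log each one with its reason, and report the unfiltered drug-related rate and its posterior probability beside the primary result.

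The prior, threshold and Table 11 need no change, and the data are already collected. The cost is more frequent holds, to the extent that events would otherwise have been excluded. The rule already holds with probability about 0.44 at a true rate of 55%, so this may not be trivial, and each hold brings a data review. Some judgment will remain in attribution and seriousness.

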12.2.2. Progression-Free Survival

Progression-free survival (PFS) is defined as the duration of time from the start of protocol treatment to first occurrence of either progressive disease or death. Disease progression can be objectively determined as per Section 11 or progression can be subjective as determined by the investigator. Evidence for subjective progression must be documented in the medical records. For objective disease progression, the date of PD is the date of the radiologic assessment that identified RECIST-defined progressive disease. For subjective disease progression, the date of PD is the date that the clinician makes the determination of disease progression. If the subject died without documented disease progression, the date of progression will be the date of death. For surviving subjects who do not have documented disease progression, PFS will be censored at the date of last radiologic assessment. For subjects who receive subsequent anti-cancer therapy prior to documented disease progression, PFS will be censored at the date of last radiologic assessment prior to the commencement of subsequent therapy. Subjects who have an initial PFS event immediately following 2 or more consecutive missed assessments will be censored at the date of the last assessment prior to those missed assessments. For participants with only one missed assessment, the documented progressive disease status and assessment date will be used.

PFS will be determined for each subject using both the RECIST 1.1 and irRECIST criteria.

12.2.3. Overall Survival

Overall survival (OS) is defined as the duration of time from the start of protocol treatment to death from any cause. Subjects who are alive or lost to

follow-up at the time of the analysis will be censored at the last known date they were alive.

12.2.4. Objective Response

Objective response will be determined for each subject as a binary variable indicating whether or not the subject achieved a best overall response of CR or PR. Objective response will be determined for each subject with measurable disease at baseline using both the RECIST 1.1 and irRECIST criteria.

12.2.5. Duration of Response

Duration of response will be determined for each subject achieving an objective response. Duration of response will be defined from time that response was initially documented until progression or death. The censoring mechanism for duration of response will be the same as that described for PFS. Duration of response will be determined for each subject using both the RECIST 1.1 and irRECIST criteria.

12.2.6. Safety Endpoints

Safety endpoints will include treatment administration (total number of doses taken, and total doses taken as a percent of total number of intended doses), AEs, SAEs, and deaths while on study therapy.

12.2.7. Second Course Objective Response

Second Course Objective response will be determined for those subjects who initiate second course treatment of pembrolizumab as a binary variable indicating whether or not the subject achieved a best overall response of CR or PR after starting second course treatment with pembrolizumab. Second Course Objective response will be determined for each subject with measurable disease at entry into Second Course Phase using both the RECIST 1.1 and irRECIST criteria.

12.2.8. Second Course Progression-Free Survival (PFS2)

PFS2 will be calculated for those subjects who initiate second course treatment of pembrolizumab in the same fashion as described in Section 12.2.2. The start date for PFS2 will be the first dose of second course treatment of pembrolizumab. PFS2 will be determined for each subject using both the RECIST 1.1 and irRECIST criteria.

12.3. Analysis Populations

All subjects starting study therapy will be included in the analysis of safety data, OS, and PFS. Objective response will be analyzed on the population of subjects who begin study treatment and have measurable disease at baseline. Duration of response will be analyzed on the population of subjects who achieve an objective response. Second course response rate and progression free survival will be conducted on subjects who initiate second course treatment of pembrolizumab.

12.4. Analysis Methods

12.4.1. Timing of Analysis

Analyses on this study will be conducted on a continuous basis in order to assess the Bayesian stopping rules for toxicity described in Section 12.5. An analysis of all endpoints will occur after the best overall response for each subject has been determined for all subjects. An updated analysis of the study will be conducted after the PFS censoring rate reduces to 20% or when all subjects have been on study at least two years (whichever occurs first). A final analysis of the study will be conducted after the overall survival censoring rate reduces to 20% or when all subjects have been on study at least five years (whichever occurs first).

12.4.2. Subject Disposition

An accounting of all consenting subjects will be provided at the end of the study. This will include a breakdown of subjects who consented, were treated, discontinued treatment, died, and were lost to follow-up or withdrew consent.

12.4.3. Baseline Subject and Disease Characteristics

A summary of subject demographics and disease-related characteristics will be completed.

12.5. Primary Analysis

A maximum of 30 evaluable subjects with soft tissue sarcoma will be enrolled as a single cohort. It is not anticipated that the addition of pembrolizumab to standard chemotherapy will increase the rate of severe or life-threatening toxicity. It has been reported that the rate of any severe or life-threatening toxicity of doxorubicin and dacarbazine every 3 weeks is 55%⁴⁸.

If it becomes evident that the rate of severe or life-threatening toxicity convincingly exceeds 55%, enrollment to the study will be halted.

The stopping rule will hold enrollment if the posterior probability of severe or life-threatening toxicity risk exceeding 0.55 is 75% or higher. In this event, data will be evaluated to inform the subsequent conduct of the study. The prior for this monitoring rule is beta (11,9). This means that our prior assumption regarding the proportion of severe or life-threatening toxicity is 0.55, and there is 90% probability that this proportion is between 0.368 and 0.726. The operating characteristics of the stopping rule are given in Table 11 and are based on 5000 simulations:

Table 11. Operating characteristics of the stopping rule

Number of Subjects with Severe or Life-Threatening Toxicities	Max. Denominator Cutoff for Early Stopping	Posterior Probability: $\Pr(\text{Risk} > 0.55 \text{Data})$
4	4	0.7834
5	6	0.7536
6	7	0.8056
7	9	0.7728
8	11	0.7694
9	13	0.7558
10	14	0.7944
11	16	0.7812
12	18	0.7592
13	19	0.8002
14	21	0.7818
15	23	0.7710
16	25	0.7594
17	26	0.7988
18	28	0.7828
19	30	0.7706

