I. Statistical Analysis	Previous reports have demonstrated that the rate of any severe or life-threatening toxicity with a median of 3 courses of doxorubicin and dacarbazine every 3 weeks is 55%. If it becomes evident that the rate of severe or life-

	
threatening toxicity convincingly exceeds 55%, the study will be halted. Response rates will be calculated with corresponding 95% confidence intervals based on the Clopper-Pearson method. Duration of response and PFS distributions will be estimated using Kaplan-Meier techniques. Exploratory correlative analyses will be conducted on biomarkers using logistic regression (response rate) and Cox proportional hazards models (duration of response and PFS). Incident rates for adverse events, SAEs, and deaths on study therapy will be summarized.

--	--

SCHEMA

* Subjects 12-17 years of age will receive pembrolizumab 2 mg/kg IV (up to 200 mg) every 3 weeks

LIST OF ABBREVIATIONS

Abbreviation	Definition of Term
AE	Adverse event
ALT	Alanine aminotransferase
aPTT	Activated partial thromboplastin time
AST	Aspartate aminotransferase
CI	Confidence interval
CHF	Congestive heart failure
CFR	Code of Federal Regulations
CNS	Central nervous system
CR	Complete response
CT	Computed tomography
CTCAE	Common Terminology Criteria for Adverse Events
CTMS	Clinical trial management system
CrCl	Creatinine clearance
DCSI	Development Core Safety Information
DNA	Deoxyribonucleic acid
DSMC	Data and Safety Monitoring Committee
eCRF	Electronic case report form
ECG	Electrocardiogram
ECI	Events of clinical interest
ECHO	Echocardiogram
ECOG	Eastern Cooperative Oncology Group
FDA	Food and Drug Administration
FSH	Follicle-stimulating hormone
GCP	Good Clinical Practice

G-CSF	Granulocyte-colony stimulating factor
GIST	Gastrointestinal stromal tumor
GMP	Good Manufacturing Practices
HIV	Human immunodeficiency virus
IB	Investigator brochure
IDS	Investigational drug services
IHC	Immunohistochemistry
INR	International normalized ratio
IRB	Institutional Review Board
irRC	Immune related response criteria
IV	Intravenous
LCI	Levine Cancer Institute
LVEF	Left ventricular ejection fraction
mAb	Monoclonal antibody
MEL	Melanoma
MRI	Magnetic resonance imaging
MUGA	Multigated acquisition scan
NSCLC	Non-small cell lung cancer
ORR	Objective response rate
OTC	Over the counter
PI	Principal Investigator
PK	Pharmacokinetics
PR	Partial response
PT	Partial thromboplastin
Q2W	Every two weeks
Q3W	Every three weeks
RCC	Renal cell carcinoma

RNA	Ribonucleic acid

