2. BACKGROUND AND RATIONALE

2.1. Study Disease

Sarcomas are a heterogeneous group of rare, malignant tumors, with over 50 histologic subtypes¹ which are generally categorized as bone and soft tissue sarcomas. The exact incidence of soft tissue sarcoma is not precisely known. A recent study in the Rhone-Alps region in France identified 748 new cases in a cohort of roughly 6 million residents². The estimated world age-standardized incidence rate was, 4.8/100,000, which was higher than previously reported (1-3/100,000). Historically, soft tissue sarcomas have been treated similarly. Doxorubicin-based chemotherapy has been the first line standard of care for more than 20 years. Adding additional cytotoxic agents (e.g. ifosfamide, dacarbazine) to doxorubicin improves response rates, but at the expense of increased toxicity and no clear increase in survival. Some histologic subtypes respond better than others. Anti-angiogenic and targeted therapies (e.g. sunitinib) to this point have been of marginal benefit in the treatment of soft tissue sarcomas. Further progress is needed.

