2.2.3. Experience with Doxorubicin

Doxorubicin is a cytotoxic antibiotic of the anthracycline family of compounds. Its cytotoxic effects are believed to stem from intercalation with DNA nucleotides and binding to cellular membrane lipids. Investigations of cellular exposure to doxorubicin have shown morphological changes associated with apoptosis. Currently, doxorubicin is the standard of care for

most subtypes of unresectable locally advanced or metastatic STS for disease which is not resectable for cure.

In the 1970s, this anthracycline was studied in a clinical trial as monotherapy directed against disseminated sarcomas.⁴⁰ Of 36 patients, 9% experienced a CR and 32% a PR. Patients who had these responses also had prolonged survival. Since then, doxorubicin has been used as single-agent therapy in the treatment of advanced and/or metastatic STS and has shown to be the most effective single agent in this setting, alternative treatments being single agent ifosfamide and more recently gemcitabine plus/minus taxotere. Comparison of doxorubicin monotherapy versus epirubicin monotherapy has shown slightly favorable response rates for doxorubicin.⁴¹ Although ifosfamide shows a similar level of effectiveness against tumor growth, doxorubicin tends to be better tolerated.⁴²

Single-agent doxorubicin has also been compared against combination therapies with and without doxorubicin. Examples include a two-arm study of doxorubicin versus the combination of vincristine plus actinomycin-D plus cyclophosphamide,⁴³ and a three-arm study of doxorubicin versus the combination therapies of doxorubicin/ifosfamide and doxorubicin/mitomycin/cisplatin as first-line treatment.⁴⁴ In the former study, doxorubicin was shown to be more effective, and in the latter, the combination treatment arms demonstrated improved response rate compared to single-agent therapy, but the doxorubicin/ifosfamide combination was significantly more myelosuppressive without a clear improvement in clinical benefit. An additional eight randomized, controlled trials have been analyzed to determine if doxorubicin combination therapy provided substantial clinical benefits compared to single-agent doxorubicin⁴⁵. With regard to response rate, survival, and toxicity across studies, it was determined that improved response rate was marginal for combination therapy, survival did not differ between the two groups, and the safety profile for combination therapy was worse than that of single-agent therapy.

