4. INVESTIGATIONAL PLAN

4.1. Overall Study Design

This is a single arm phase II study designed to investigate the safety, tolerability, and preliminary efficacy of the combination of pembrolizumab and doxorubicin in subjects with metastatic/unresectable soft tissue sarcoma. Following informed consent and eligibility check, all enrolled subjects will receive therapy with doxorubicin and pembrolizumab.

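### The 55% toxicity benchmark comes from doxorubicin plus dacarbazine, so a rate at or below it cannot show that pembrolizumab adds no severe toxicity to doxorubicin

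*Combined protocol and SAP*

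**What the plan says.** The primary objective (section 1.1) is to estimate the severe and life-threatening toxicity rate in subjects "treated with doxorubicin and pembrolizumab, and compare to historical control". Section 4.1 confirms the regimen: "all enrolled subjects will receive therapy with doxorubicin and pembrolizumab". No other cytotoxic is given.

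The historical figure is identified in two places. The Protocol Summary (Statistical Analysis) says "the rate of any severe or life-threatening toxicity with a median of 3 courses of doxorubicin and dacarbazine every 3 weeks is 55" percent. Section 12.5 repeats it without the exposure: "the rate of any severe or life-threatening toxicity of doxorubicin and dacarbazine every 3 weeks is 55" percent. Section 12.1 justifies 30 subjects by whether the rate convincingly exceeds 0.55. Section 12.5 holds enrolment if the posterior probability of a rate above 0.55 reaches 75%, using a Beta(11,9) prior.

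Section 12.5 also states the expectation behind the comparison: "It is not anticipated that the addition of pembrolizumab to standard chemotherapy will increase the rate of severe or life-threatening toxicity".

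The background sections rank the regimens. Section 2.1: "Adding additional cytotoxic agents (e.g. ifosfamide, dacarbazine) to doxorubicin improves response rates, but at the expense of increased toxicity". Section 2.2.3, on eight randomized trials: "the safety profile for combination therapy was worse than that of single-agent therapy". Section 2.2.3 also describes doxorubicin as the standard of care for most subtypes.

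**The concern.** The expectation in 12.5 concerns what pembrolizumab adds to the chemotherapy given here, which is doxorubicin. The reference rate belongs to doxorubicin plus a second cytotoxic that the protocol itself describes as adding toxicity. The same rate serves as hold threshold, prior mean and basis for the sample size.

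What is at stake is how a reassuring result may be read. If the trial finishes with a rate at or below 55%, the plan has compared the combination with doxorubicin-dacarbazine. It has not compared it with doxorubicin. The 12.5 sentence about standard chemotherapy invites the second reading, and the plan gives no reason for choosing the doublet as reference.

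**Working it through.** **Inputs from the plan (12.5).** Prior Beta(11,9), threshold 0.55, posterior cut-off 0.75, maximum 30 subjects. Section 12.4.1 says the rule is assessed continuously; I take a look after every subject.

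**Step 1: reproduce the plan's figures.** The prior mean is 11/(11+9) = 0.55. The exact 90% prior interval is 0.368 to 0.726, as stated. With k events in n subjects the posterior is Beta(11+k, 9+n−k). Exact values of Pr(rate > 0.55):

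| Events/subjects | Table 11 | Exact |
|---|---|---|
| 4/4 | 0.7834 | 0.7797 |
| 7/9 | 0.7728 | 0.7865 |
| 9/13 | 0.7558 | 0.7488 |
| 19/30 | 0.7706 | 0.7671 |

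All 16 printed posteriors agree within 0.014, and 15 of the 16 boundaries match. The exception is 9/13, whose exact value falls just under 0.75, so the exact cut-off is 9/12. Monte Carlo error with 5000 draws is about 0.006, which covers a slip of that size. The arithmetic is sound; the issue is what 0.55 represents.

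**Step 2: probability of a hold.** Table 11 lists boundaries and posteriors, but not how often the rule would act. Let q_n(k) be the probability of k events after n subjects with no hold so far, at true rate p. Then q_n(k) = (1−p)·q_{n−1}(k) + p·q_{n−1}(k−1). After each n, any k with posterior at or above 0.75 is removed and its probability added to P(hold).

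| True rate | 0.30 | 0.35 | 0.40 | 0.45 | 0.50 | 0.55 | 0.60 | 0.65 | 0.70 |
|---|---|---|---|---|---|---|---|---|---|
| P(hold) | 0.019 | 0.041 | 0.084 | 0.159 | 0.277 | 0.438 | 0.622 | 0.792 | 0.912 |

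Using the boundaries exactly as printed moves these by less than one percentage point (0.446 at 0.55).

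**Step 3: what that means for added toxicity.** The documents give no severe-toxicity rate for doxorubicin alone. I assume 0.30 to 0.50, and an illustrative rise of 15 points on adding pembrolizumab. The last two columns apply the same rule centred on the assumed rate, with prior weight 20 as in Beta(11,9).

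| Assumed doxorubicin rate | With pembrolizumab | P(hold), current rule | P(no hold), current rule | P(hold), re-centred, 15-point rise | P(hold), re-centred, no rise |
|---|---|---|---|---|---|
| 0.30 | 0.45 | 0.159 | 0.841 | 0.877 | 0.366 |
| 0.35 | 0.50 | 0.277 | 0.723 | 0.889 | 0.393 |
| 0.40 | 0.55 | 0.438 | 0.562 | 0.888 | 0.402 |
| 0.45 | 0.60 | 0.622 | 0.378 | 0.902 | 0.438 |
| 0.50 | 0.65 | 0.792 | 0.208 | 0.896 | 0.420 |

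The current rule is insensitive to a 15-point rise if the single-agent rate is about 0.40 or lower, and reasonably sensitive if it is near 0.50. Re-centring gains sensitivity, but it holds 37% to 44% of the time when pembrolizumab adds nothing.

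**The case against.** **The plan never declares safety at or below 55%.** This stands. A reader might infer a built-in lean towards calling the combination safe, but no section contains such a criterion. Section 12.1 asks only whether the rate convincingly exceeds 0.55, and a hold leads to data review. A ceiling taken from an earlier two-drug regimen is a legitimate choice. The plan does not say it is making that choice, and the sentence on standard chemotherapy points elsewhere.

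**The 55% may not overstate the rate expected here.** This stands in part. A reader might infer that the benchmark is too high for this trial, but sections 2.1 and 2.2.3 rank regimens only qualitatively. The benchmark exposure was a median of 3 courses. Here the 450 mg/m² cap allows seven full doses at 60 (450/60 = 7.5), or six if escalated after the first (60 + 5×75 = 435). Section 3.2.1 accepts any number of prior systemic therapies. Both could raise the rate. Against that, section 12.2.1 counts only serious, drug-related events that the Sponsor-Investigator judges should count, which could lower it. The net direction is uncertain, which is a further reason not to read a rate below 55% as a verdict on pembrolizumab.

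**Added toxicity would not go unnoticed.** This stands. Adverse events are attributed to each drug (10.3), reviewed regularly with data sent to the DSMC (8.1) and summarised (12.7). The study can be stopped on risk-benefit grounds (13.2). The hold rule is one layer among several.

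**The comparison is not uninformative.** This also stands. A rate well above 55% would, on the protocol's own ordering, also exceed single-agent doxorubicin. A hold alone is weaker evidence: at an assumed single-agent rate of 0.50 with no pembrolizumab effect, it still occurs 28% of the time.

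**Conclusion.** The point holds as a limit on inference. The threshold and prior mean come from a doublet that the protocol describes as more toxic than doxorubicin alone. A rate at or below 55% therefore supports only the conclusion of not convincingly more toxic than doxorubicin-dacarbazine, and leaves the 12.5 expectation about pembrolizumab untested.

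The hold probabilities follow exactly from the plan's rule with a look after each subject. Their translation into missed increases (72% without a hold for 0.35 to 0.50, 56% for 0.40 to 0.55) rests on assumed single-agent rates and an assumed 15-point rise. The true size of the mismatch cannot be computed from the documents.

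A reader might go further and conclude that the hold rule must be re-centred on a single-agent rate. The documents do not support that. They contain no such rate, and the re-centred rule at an assumed 0.40 with a Beta(8,12) prior would hold about 40% of the time with no added toxicity. That is a trade-off for the sponsor to weigh.

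**What to change.** 1. In 1.1, 12.1 and 12.5, name doxorubicin-dacarbazine as the historical control and describe 55% as a tolerability ceiling. State that a rate at or below it does not show that pembrolizumab adds no toxicity to doxorubicin. Carry the median of 3 courses from the Protocol Summary into 12.5 as a caveat on comparability.
2. Remove or reword the 12.5 sentence on the expected effect of adding pembrolizumab.
3. In the primary analysis, report the observed rate with an interval, and the posterior probability that it exceeds each of a range of assumed single-agent reference rates, for example 0.30 to 0.50. State the prior used, since Beta(11,9) is itself centred on the doublet. If the single-agent arms of the studies already cited report a rate under a comparable definition, use that; whether they do cannot be seen from the documents.
4. Add P(hold) by true rate to Table 11.
5. Re-centring the hold rule is optional. If it is considered, show its hold probability with no added toxicity beside its sensitivity.

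The cost is protocol and SAP wording, a little extra analysis and a less favourable safety statement. No patients or procedures are added.
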